#### 3. Study Procedures

### a. Study design, including the sequence and timing of study procedures (distinguish research procedures from those that are part of routine care).

Study design: For this revised study protocol we will randomize 80 participants to complete a 13-week cognitive-behavioral therapy treatment protocol involving either a single high-dose (30mg/70kg) administration of psilocybin, or an 8 to 10 week course of NRT (transdermal nicotine patch) for smoking cessation. Participants will be nicotine-dependent cigarette smokers, who have had multiple unsuccessful quit attempts, and who continue to desire to quit smoking. Other than nicotine dependence, participants will be physically and psychologically healthy. In total, 95 participants will complete the study, including 15 individuals who have already completed psilocybin-facilitated treatment before the current protocol modifications, and 80 further individuals to be recruited for the revised study design including NRT control arm. Fifty participants will also undergo MRI data collection before and after treatment to inform neurobiological mechanisms of action. After screening and enrollment, participants will complete several baseline measures, and those who have consented to participate in the MRI scanning component will be invited to participate in an optional NIDA sub-study protocol. Participants will begin a 13-week cognitive-behavioral smoking cessation program consisting of weekly meetings with two trained study staff members for weeks 1-7 of study treatment, and meetings every other week thereafter (i.e., weeks 9, 11, and 13). For the revised study protocol up to 60 participants will undergo an MRI scan in week 2 of study treatment, and will be required to abstain from smoking for 24 hours before all MRI scans as verified by breath carbon monoxide measures. An additional 30 individuals who do not meet MRI scanning inclusion criteria (e.g., are left handed), but are otherwise eligible to enroll, will complete only the treatment-related portions of the study. During the third treatment meeting in week 3, participants will be randomized into one of two treatment conditions (i.e., psilocybin or NRT).

After randomization, the 40 participants assigned to the psilocybin condition will receive specialized preparation for their psilocybin session in treatment meetings 3 and 4. They will then be administered 30mg/70kg psilocybin on their mutually agreed upon Target Quit Date (TQD) in approximately week 5. These participants will meet with study staff the day after their psilocybin session for debriefing, and 25 of these will additionally complete a 4-6 hour post-psilocybin MRI scan that day. Treatment meetings will continue weekly for two weeks after the psilocybin session, and at 2-week intervals from weeks 9 through 13 to discuss the session experience and to provide support for smoking cessation. Participant smoking status will be assessed repeatedly at five meetings after the psilocybin session using self-report and breath carbon monoxide (CO) samples. Smoking status will also be assessed at three follow up meetings approximately 3, 6, and 12 months after the psilocybin session using self-report, breath, and urine samples. All study meetings will have the option to be completed remotely using a secure online format, including remote breath CO monitoring and mailed in or at home urine sample tests, with the exception of physical examination during initial screening, psilocybin sessions, and MRI scan procedures.

After randomization, the 40 participants in the NRT condition (matched for age, sex, IQ, and smoking severity) will receive specialized preparation for NRT administration. In approximately week 5, these participants will begin a standard 8 to 10 week NRT treatment regimen according to recommended label usage (For individuals who smoke more than 10 cigarettes per day: 21mg daily weeks 1-6, 14mg daily weeks 7-8, 7mg daily weeks 9-10. For individuals who smoke 10 or less cigarettes per day: 14mg daily for weeks 1-6, 7mg daily for weeks 7-8; FDA label, PDR.net). Participants in the NRT condition will have brief weekly counseling meetings and provide exhaled CO samples to test for smoking status in weeks 6, 7, 9, 11, and 13. These individuals will also have follow-up meetings at approximately 3, 6, and 12 months post target-quit date to assess smoking status. Participants randomized to the NRT condition who are also completing the MRI portion of the study (n=25) will complete their second MRI scan in week 5, immediately before initiating use of the nicotine patch. For both treatment conditions, MRI participating volunteers who provide biologically verified (i.e., breath CO), and self-report seven-day point prevalence abstinence at 3 months post-TQD will receive a final follow-up MRI scan.

After completing the 6-month follow-up, participants initially randomized to the NRT condition (n=40) will be given the option to undergo a single high-dose (30mg/70kg) psilocybin session. If they choose to take part, they will receive two weekly preparation meetings, one psilocybin session and next-day integration meeting, and two weekly follow-up meetings. For individuals still smoking at that time, the session will serve as an additional quit attempt and provide further data on psilocybin-facilitated smoking cessation. For participants who are no longer smoking, the session will focus on promoting long-term abstinence. The rationale for offering an optional psilocybin session to all participants in the NRT condition is twofold. Firstly, we hope to reduce differential dropout among participants randomized to the NRT condition, and encourage them to complete study treatment through 6-month follow-up. Secondly, in offering this optional session to those who were both successful and unsuccessful in quitting smoking using NRT, we can avoid encouraging poor treatment compliance in the NRT condition (i.e., intentionally failing to quit smoking in order to receive additional treatment with psilocybin). For participants from the NRT condition who choose to take part in the optional psilocybin session, the remaining long-term follow-up meeting will be shifted to take place at 6 months after their psilocybin session (in place of their original 12-month follow-up). For participants from the NRT condition who decline to take part in the optional psilocybin session, study follow-ups will proceed as originally planned at 12 months after their originally assigned Target-Quit Date.

**Volunteer Accrual and Screening:** Potential participants will learn of the protocol by posted, and internet-posted notices, newspaper advertisements, and word of mouth referral. Volunteers will be screened via a secure online screening questionnaire hosted on a Johns Hopkins approved Qualtrics account and/or telephone to determine whether they meet major inclusion/exclusion criteria, and thus whether they are eligible for an in-person screening session. Individuals will not sign consent before telephone screening. It would not be practical to mail individuals a consent form for the telephone screen because we believe that individuals could find this inconvenient and would not respond, and also that some individuals might be unwilling to provide their mailing address. Individuals who do not pass online / telephone screening or choose not to participate will be asked whether they want us to keep their personal contact information. If the volunteer agrees, this information will be added to an existing approved research database established with application number: BPRU00-01-31-02. Identifiers for those individuals who do not want us to retain their information will be destroyed. The rationale for

having the research database is that we want to be able to summarize the reasons that individuals failed screening or choose not to participate in this study, and we want to be able to contact individuals who might qualify for future studies. We anticipate that this protocol could be one of a set of studies with psilocybin and related hallucinogens that would continue for at least the next 5 years. Because the inclusion/exclusion criteria may be changed in the future, it is possible that excluded volunteers may be eligible for studies in the future.

Volunteers who do not fail online / telephone screening will be invited to the BPRU on the Johns Hopkins Bayview Campus for in-person screening. Individuals who complete an online / telephone screening and do not meet the following specific MRI-related study inclusion criteria, will still be eligible to screen and enroll in the treatment portion of the study. This includes individuals who: a) are left-handed; b) may have magnetic/metallic materials in their body; c) suffer from claustrophobia; d) are over 65 years of age; and e) indicate they do not have sufficient free time to complete the MRI related tasks, but would otherwise be available to complete the treatment portion of the study.

Volunteers who fail screening at BPRU but who, in the judgment of the investigators, might be eligible for a future study will be asked to complete IRB-approved HIPAA-IRB Form 3 "Authorization to contact you about future research studies." Volunteers' files will be kept in a locked room and treated as confidential research material. All data will be collected using the unique identification code numbers assigned to each volunteer upon entry to the study. No individual identifiable information will be released without written authorization. These procedures have been used in the past to protect confidentiality of study data and no instance of loss of confidential information has occurred.

Two hundred volunteers will sign consent to be screened to provide 130 participants who start the study, and 115 participants to participate until completion. Consent will be obtained at BPRU at a scheduled meeting after volunteers have passed telephone screening. Due to COVID-19 space restrictions, participants and study staff may review the consent form remotely or onsite in separate rooms over a secure online platform (e.g., Zoom) to go over study procedures and answer questions before signing consent. Informed consent will be signed at BPRU in-person. Participants will be provided an information sheet about COVID-19 per JH SOM Research Visit Guidelines, as well as information about personal protective equipment (PPE) requirements for their upcoming visit. Participants will be encouraged to socially distance per national and regional guidelines. Written informed consent will be updated to reflect the measures described herein.

Participants will complete a pre-visit COVID-19 symptom questionnaire within 24 hours of all in-person visits, and/or be screened with a symptom questionnaire upon arrival at the Behavioral Pharmacology Unit (BPRU). The screening questionnaire will assess for possible COVID-19 symptoms including:

- Elevated body temperature
- Presence of cough
- Loss of smell or taste
- Presence of fatigue or general malaise
- Presence of headache
- Presence of body aches
- Adherence to social distancing guidelines
- Known contact with an individual who tested positive for COVID-19 in the past 14 days

• Engagement in high-risk behaviors (e.g. participation in large gatherings without social distancing or use of PPE)

The screening questionnaire may be subject to change based on new information about COVID-19. Body temperature measurement will also occur upon arrival at the BPRU.

Participants will be allowed to take as much time as necessary to decide whether or not to sign consent. Study staff will discuss the consent form with the volunteer after they have read the consent form, as well as providing the recruitment materials for the optional NIDA sub-study protocol to be reviewed at the time of enrollment for individuals who are eligible for MRI scanning. Study staff will ask participants to read a paragraph from the consent form out loud to assess English literacy and will ask questions regarding basic study procedures to assess the individual's understanding of the consent forms. Participants may take the consent forms home to review and return to sign consent if they wish. Non-English speakers and those with language or hearing impairments will not participate in the study. Participants will be physically and psychologically healthy adult volunteers (approximately equal numbers of males and females). Participants completing the MRI scanning portion of the protocol at NIDA must be between the ages of 21 and 65 years old. For those who will not be completing MRI scanning at NIDA (treatment only), volunteers ages 21 to 80 may participate. We expect to locate participants who are both qualified and motivated to adhere to the rigorous conditions of the study. Participants may or may not have used hallucinogens in the past. Our ongoing trial, as well as considerable data from prior studies, documents the safety of administering psilocybin at the proposed dose level to participants without histories of hallucinogen use. However, to attenuate the possibility of non-optimal response in individuals with higher body weight, this study will use an absolute maximum dosage of 50 mg, which is approximately equivalent to absolute doses we have administered safely to heavier participants in previous studies.

Potential participants will be carefully screened to eliminate those with significant medical or psychiatric illnesses. Evaluation will include a history and physical examination, CBC, SMA-24 (or equivalent), ECG, and urine drug test. Participants will also be requested to refrain from illicit drug use during the course of the study and a urine test will be conducted before the administration of psilocybin. Left-handed individuals are ineligible for MRI scanning, but may otherwise complete the study treatment. Pregnant or nursing women are ineligible; female participants will receive a urine pregnancy test at intake and before psilocybin administration, and must use effective methods of contraception during the study. Other medical exclusion criteria are presented in section 5. With regard to psychiatric screening, based on clinical interviews and a structured psychiatric diagnostic interview, participants will be eligible if they are judged to be psychologically stable and do not meet any of the psychiatric exclusion criteria (as defined by DSM-IV) presented in section 5. Psychiatric screening interviews may take place remotely via secure online platform.

Meetings Before and After TOD (Psilocybin Condition): Before the psilocybin session day participants in the psilocybin condition will meet with one or more of the study staff on at least 3 occasions, for a minimum of 4 hours of contact time before the session day. Some flexibility in scheduling will be allowed to account for unexpected absences such as travel commitments or illnesses. The main purpose of the participant-staff meetings is to develop rapport and trust, which we believe helps minimize the risk of fear or anxiety reactions during the psilocybin session. Additional meetings and contact hours (up to 10 hours) will be scheduled if it is judged necessary to establish rapport and trust. The participant's life history and current situation in life will be reviewed.

Timeline a	Psilocybin condition meetings (duration)	NRT condition meetings (duration)
	Screening Day 1/ C	Consent (6 hrs)
	Screening Day 2 (2-3 hrs)	
-	Optional NIDA sub-study protocol / MRI Scan 1 (6-8 hrs)*	
	MRI task training at NIDA (2-3 hrs)*	
	Treatment meeting 1 (1-2 hrs)	
Week 1	Study orientation	
	Assign Target Quit	Date (TQD)
	Sign contract to quit / smoking diary introduction	
	MRI scan 2 (4-5 hrs)*	
	Treatment meeting 2 (1-2 hrs) Carbon monoxide demonstration	
Week 2		
	Smoking financial costs	
	Identifying motivation to quit	
	Treatment meeting 3 (90 min)	Treatment meeting 3 (90 min)
	Randomization to treatment condition	Randomization to treatment condition
Week 3	Discuss previous quit attempts	Discuss previous quit attempts
	Weight gain and quitting smoking	Weight gain and quitting smoking
	Recovery symptoms	Recovery symptoms
	Discussing psilocybin effects	Discussing NRT effects
	Treatment meeting 4 (90 min)	Treatment meeting 4 (90 min)
	Smoking diary discussion	Smoking diary discussion
Week 4	Dealing with urges after TQD	Dealing with urges after TQD
	Preparing to quit	Preparing to quit
	What to expect in psilocybin session	How to take NRT
	Psilocybin session / TQD (8 hrs)	MRI scan 3 / TQD (4-6 hrs)*
Week 5	MRI scan 3 (4-6 hrs; Next day)*	Treatment meeting 5 (1-2 hrs)
	Treatment meeting 5 (1-2 hrs; Next day)	Initiation of NRT
	Participant Narrative of Session	
	Treatment meeting 6 (45 min)	Treatment meeting 6 / TQD (45 min)
Week 6	Identifying triggers	Identifying triggers
	Overcoming urges to smoke	Overcoming urges to smoke
	Treatment meeting 7 (45 min)	Treatment meeting 7 (45 min)
Week 7	Supporting smoking abstinence	Supporting smoking abstinence
	Treatment meeting 8 (45 min)	Treatment meeting 8 (45 min)
Week 9	Supporting smoking abstinence	Supporting smoking abstinence
	Treatment meeting 9 (45 min)	Treatment meeting 9 (45 min)
Week 11	Supporting smoking abstinence	Supporting smoking abstinence
W. 1.10	Treatment meeting 10 (45 min)	Treatment meeting 10 (45 min)
Week 13	Clinical interview	Clinical interview
3 months post-TQD	Follow-up meeting (2-4 hrs)	Follow-up meeting (2-4 hrs)
	MKI Scan 4 ° (4-6 hours)*	MRI Scan 4° (4-6 hours)*
6 months post-TQD	Follow-up meeting (2-4 hrs)	Follow-up meeting (2-4 hrs)
12 months post-TOD	Follow-up meeting (2-4 hrs)	Follow-up meeting (2-4 hrs)

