In total, 115 participants will complete this pilot study. Fifteen individuals have already undergone the initially approved protocol with no clinically significant adverse events. A further 100 participants will be randomized to a psilocybin condition or a nicotine replacement therapy (NRT; i.e., transdermal nicotine patch) condition, 60 of whom will be studied with functional neuroimaging procedures. The NRT condition will serve as an important control for evaluating relative efficacy of the psilocybin condition, as well as examining differences in neuroimaging results. After screening and enrollment, individuals who are eligible for MRI scanning (n=60) will be invited to complete an optional preliminary sub-study protocol consisting of a 6-8 hour MRI scan, blood draw, and questionnaire assessment at the National Institute on Drug Abuse (NIDA) Intramural Research Program on the Johns Hopkins Bayview Campus. After completing the sub-study protocol, or opting out, participants will begin a 13-week cognitive-behavioral smoking cessation intervention, with Target Quit Date (TQD) set in approximately week 5. Participants who are eligible for and willing to participate in MRI scanning (n=60), will have MRI scans conducted in weeks 2 and 5, and at 3-month follow-up for those participants who have maintained smoking abstinence to that point. Individuals who do not meet MRI scanning inclusion criteria, but are otherwise eligible to enroll (n=40), will complete only the treatmentrelated portions of the study.

During the third treatment meeting in week 3, participants will be randomized into one of two treatment conditions (i.e., psilocybin or NRT). In one condition a single high-dose

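### The protocol gives two randomised sample sizes, 100 and 80, each with its own dependent counts, and does not say which one governs

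*Combined protocol and SAP*

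**What the plan says.** The text supports two sets of numbers.

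**The 100 set.** The Abstract says "A further 100 participants will be randomized to a psilocybin condition or a nicotine replacement therapy" and "In total, 115 participants will complete this pilot study", the latter including 15 people treated under the earlier single-arm protocol. It divides the 100 into 60 with MRI and 40 without. Section 3a, Volunteer Accrual and Screening, expects 130 to start and 115 to complete. Section 3a, MRI Brain Scanning Sessions, gives 30 MRI participants per group, up to 60 in all. Section 3b repeats 60 and 40. An MRI count of 60 also appears in the footnote to the Section 3a meeting table, in Baseline and Follow-up Data Collection, in the footnote to the Section 6b measures table, and in Section 9a.

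**The 80 set.** The opening paragraph of Section 3a says "For this revised study protocol we will randomize 80 participants to complete a 13-week cognitive-behavioral therapy treatment protocol" and "In total, 95 participants will complete the study". It adds "Fifty participants will also undergo MRI data collection before and after treatment" and "An additional 30 individuals who do not meet MRI scanning inclusion criteria". The next paragraphs give arm sizes: "After randomization, the 40 participants assigned to the psilocybin condition" and "After randomization, the 40 participants in the NRT condition", with 25 MRI participants in each arm. The 40 for the NRT arm is repeated where the optional later session is described. The NRT Condition text in Section 3a divides that arm into 25 with MRI and 15 without.

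Section 6c gives no sample size, alpha, power or expected abstinence rate.

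**The concern.** Section 3a contains both sets, and its opening paragraph mixes them: it gives fifty MRI participants in one sentence and a ceiling of 60 a few sentences later. No sentence gives one set precedence, and the statistical section, where a reader would look for the answer, is silent.

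Three things cannot be read from the protocol as a result: when enrolment stops, how precise the primary comparison is meant to be, and how many people enter each arm and the MRI component. Section 3c says the trial is unblinded. With two totals on paper, stopping at 80 or continuing to 100 could each be defended from the text after outcomes have begun to accrue. Section 6c plans no interim analyses, but that statement means less when the final number is not fixed.

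The protocol calls itself a pilot and states no power target, so no power claim is shown to be false. The defect is that the planned size is undefined.

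**Working it through.** **1. Does each set add up?**

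| Check | 100 set | 80 set |
|---|---|---|
| Earlier participants + randomised = completers | 15 + 100 = 115 | 15 + 80 = 95 |
| MRI + treatment-only = randomised | 60 + 40 = 100 | 50 + 30 = 80 |
| MRI per arm × 2 | 30 × 2 = 60 | 25 × 2 = 50 |
| Arm size × 2 | not stated | 40 × 2 = 80 |
| NRT arm, MRI + treatment-only | not stated | 25 + 15 = 40 |

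Both sets pass, so this is more than one mistyped digit. If the ceiling of 60 in the opening paragraph of Section 3a is combined with the 30 treatment-only participants in the same paragraph, the total is 90, which matches neither version.

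**2. Could 80 be the completers from 100 randomised?** Both sentences use the word for randomisation, and both completer totals count everyone randomised as completing. The accrual figures allow a further check, using required number = completers / (1 − loss).

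- Loss from 130 starters to 115 completers: 15/130 = 11.5%. Then 80 / (115/130) = 90.4, so 91.
- Loss after removing the 15 earlier participants from both figures, 115 to 100: 15/115 = 13.0%. Then 80 / (100/115) = 92.
- Reaching 100 from 80 needs a loss of 1 − 80/100 = 20%, which is stated nowhere.

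Dropout does not reconcile the figures.

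**3. What the difference means for precision.** With equal arms, the standard error of a difference in proportions scales as 1/√n. Going from 40 to 50 per arm multiplies the confidence interval width by √(40/50) = 0.894, a reduction of 10.6%, whatever the abstinence rates. The 40 per arm is written in Section 3a. The 50 per arm is not written and is inferred here from equal allocation.

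**4. Illustration under assumed rates.** The protocol states no rates, alpha or power, so all four rate pairs and the two-sided 5% level are assumptions. Half-width = 1.96 × √[p₁(1 − p₁)/n + p₂(1 − p₂)/n]. For 50% against 25% at 40 per arm: 1.96 × √(0.25/40 + 0.1875/40) = 1.96 × 0.1046 = 20.5 points. Power is by full binomial enumeration of the Wald test of the log odds ratio, which corresponds to the planned logistic regression with treatment as the only predictor. Tables with a zero cell are counted as non-significant.

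| Assumed abstinence | Power, 40 per arm | Power, 50 per arm | Half-width, 40 | Half-width, 50 |
|---|---|---|---|---|
| 50% vs 25% | 65% | 74% | 20.5 | 18.3 |
| 45% vs 20% | 67% | 76% | 19.8 | 17.7 |
| 40% vs 20% | 50% | 58% | 19.6 | 17.5 |
| 50% vs 30% | 46% | 54% | 21.0 | 18.8 |

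Across these cases power differs by 8 to 10 percentage points and half-width by about 2 points.

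**The case against.** The strongest reply is that the answer is visible: 100 is the live figure and 80 is text that was not updated. The only accrual statement, with 115 completers, agrees with 100. The 60 MRI count recurs across several sections, while the 80 set is confined to the design paragraphs and the NRT Condition text in Section 3a. This is plausible, but it remains an inference. The paragraph giving 80 describes itself as the revised protocol, and the only total arm size written anywhere is 40. A reader who looks up the size of an arm finds only the smaller version.

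A second reply is that a ceiling of 60 for MRI does not contradict fifty. That is correct where the text says up to 60. It does not help where 60 is stated outright, nor with 80 against 100, 95 against 115, or 30 against 40 treatment-only participants.

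A third is that this is a small pilot whose endpoint and analysis method do not depend on the total. That is also true, and it is why no failed power claim is alleged. But Section 2 says the results will indicate whether a larger trial is warranted, and their precision depends on the number randomised.

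A further gap affects either version. If the 130 starters include the 15 earlier participants, there are 115 new starters against 100 randomised. Losses before the week 3 randomisation could account for this, but the protocol does not say so.

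**Conclusion.** The concern holds. The current text gives two incompatible randomised totals, 80 and 100, with dependent counts that are consistent within each set and conflict between them. Nothing in the protocol settles which applies, and dropout does not explain the difference. The gap is 20 randomised participants and 10 MRI participants. On the assumption of equal allocation at 100, that is 40 against 50 per arm and a confidence interval about 10.6% narrower at the larger size. The power figures rest on assumed rates and only illustrate scale; the conclusion does not depend on them. This should be corrected, because the size of the primary comparison is something the trial relies on and it is currently undefined.

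**What to change.** State one target as the number randomised, with explicit per-arm numbers and the allocation ratio. Keep it separate from the 15 earlier single-arm participants, and give expected completers as a distinct figure. Put the number in Section 6c and say that enrolment stops there.

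- **If 100 is intended:** correct the study design paragraphs and the NRT Condition text in Section 3a to 100 randomised, 60 MRI and 40 treatment-only. With 1:1 allocation, which should be written, this is 50 per arm: 30 MRI and 50 − 30 = 20 treatment-only.
- **If 80 is intended:** correct the Abstract; in Section 3a, the ceiling of 60 in the opening paragraph, the accrual text, the meeting-table footnote, MRI Brain Scanning Sessions, and Baseline and Follow-up Data Collection; Section 3b; the measures-table footnote and Functional Neuroimaging text in Section 6b; and Section 9a. The figures are 40 per arm (25 MRI, 15 treatment-only), 50 MRI and 30 treatment-only overall, and 95 completers including the earlier 15.

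Under either choice, recheck the screening and starter numbers in the accrual text and say whether the 130 starters include the earlier 15.

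The cost is a wording amendment. The choice itself has a size: 100 is 20 more randomised participants than Section 3a states, and 80 is 20 fewer than the Abstract states.
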